3.3.3 Protocol Stopping Rules

This study will utilize the Common Terminology Criteria for Adverse Events (CTCAE) version 4.0 for grading systemic toxicity. For safety reasons, the protocol will be temporarily halted pending discussions with the NCI IRB and Sponsor regarding necessary amendment for either of the following events:

- One occurrence of grade 5 toxicity by the NCI-CTCAE version 4.0 attributable to the treatment regimen.
- Two occurrences of grade 4 toxicity by the NCI-CTCAE version 4.0 attributable to the treatment regimen.

3.3.4 Re-Induction

Patients who entered the maintenance phase and have confirmed PD (per immune-related RECIST criteria) during the maintenance treatment may be eligible to receive re-induction therapy using Tremelimumab at the assigned dose and schedule: i.e. 10mg/kg monthly for 6 months followed by maintenance 3-monthly Tremelimumab. Patients who stopped maintenance treatment because of a CR and subsequently had confirmed PD (per immune-related RECIST criteria) are eligible to receive re-induction as well. Subjects with an initial PR or CR or SD for at least 3 months and subsequently have PD are also eligible for re-induction. As part of re-induction they will also undergo the repeat ablative procedure on Day 36 (+/- 96hrs). This may be either an RFA or TACE depending on the opinion of the interventional radiologist. To be eligible for re-induction patients must satisfy the criteria stated in section 2.1.3.

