- 2.1.2.13 HIV-positive patients receiving anti-retroviral therapy are excluded from this study due to the possibility of pharmacokinetic interactions between antiretroviral medications and Tremelimumab. HIV positive patients not receiving antiretroviral therapy are excluded due to the possibility that Tremelimumab may worsen their condition and the likelihood that the underlying condition may obscure the attribution of adverse events.
- 2.1.2.14 History of hypersensitivity reaction to human or mouse antibody products.
- 2.1.2.15 Pregnancy and breast feeding are exclusion factors. The effects of Tremelimumab on the developing human fetus are unknown. Enrolled patients must agree to use adequate contraception (hormonal or barrier method of birth control; abstinence) prior to study entry, the duration of study participation and 3 months after the end of the treatment. Should a woman become pregnant or suspect she is pregnant while she or her partner is participating in this study, she should inform her treating physician immediately.
- 2.1.2.16 Patients with unhealed surgical wounds for more than 30 days.
- 2.1.3 Re-Induction Criteria (if applicable)
 - 2.1.3.1 Subjects must have entered the Maintenance Phase and are under ongoing maintenance treatment
 - or** Subjects who stopped maintenance treatment because of a CR
 - or** Subjects with an initial PR or CR or at least 3 months of SD on tumor assessment
 - and** who subsequently have a confirmed and documented disease progression (per immune-related RECIST criteria).
 - 2.1.3.2 Patients are excluded from re-induction if they have experienced any related Dose-limiting toxicities as described in Section 3.6, delayed dosing beyond 35 days due to Tremelimumab-related AEs, or have been taken off treatment due to toxicity as described in Section 3.8.3.

2.1.3.3 Patients who have progressed on initial therapy will not be considered for re-induction treatment.

2.1.3.4 Tremelimumab Dose: Patients will be treated at the same dose of Tremelimumab as they previously received. For patients on Dose Level 1 who had already satisfied criteria for escalation to 10mg/kg they will be re-treated at 10mg/kg.

2.1.3.5 The patient must – at the time of re-induction – satisfy all the eligibility criteria as set out in Sections **2.1.1** & **2.1.2**.

2.1.3.6 The patient must be discussed at GI Tumor Board, NCI and suitability for the interventional procedure (TACE or RFA) re-affirmed.

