3 STUDY IMPLEMENTATION

3.1 STUDY DESIGN

- The proposed study is a pilot study of Tremelimumab - at a planned dose 10mg/kg/IV q 4 weekly - in patients with advanced HCC treated with either TACE or RFA.

The initial study population is Cohort A as described below and these patients will be treated with either RFA or TACE. The decision on which treatment to administer (i.e. RFA vs. TACE) will be made in consultation with the interventional radiologists. The reason for this is that there are technical considerations (size and location of lesion, main portal vein occlusion etc.) which would make one procedure preferable over the other.

Cohort	Population	Immune stimulative procedure	Dose level (Trem)	Planned N
A	Advanced HCC, BCLC Stage C	RFA/TACE	3.5mg/kg	3-6
			10mg/kg	20
B	Intermediate HCC, BCLC B	TACE	10mg/kg	20

- Transarterial chemoembolization is percutaneous procedure performed under general anesthesia or conscious sedation. (See 3.9.1 for details)
- Patients undergoing trans-arterial chemoembolization, RFA or cryoablation are pre-medicated with analgesics, antibiotics and anti-emetics per clinical standards. For details regarding each procedure please see 3.9.
- We will also enroll an additional cohort of N=20 patients (Cohort B) with liver-confined disease for whom TACE is indicated as standard of care. These patients will receive TACE in combination with Tremelimumab using the same schema, although for these patients TACE may be repeated (as per standard of care). They will not receive RFA.
- With protocol amendment F, it was proposed that once cohort A has demonstrated safety and feasibility for the combination of ablative treatment and tremelimumab in HCC, we will add 3 additional cohorts (C-E) to the study. However, with amendment I we have revised the study design to remove Cohort C, so only 2 cohorts, D and E, remain. For these cohorts, the schedule of administration for tremelimumab and the timing of the immune-stimulative procedure is identical to cohorts A and B, as summarized below.

Cohort	Population	Immune stimulative procedure	Dose level (Trem)	Planned N
D	Advanced HCC, BCLC Stage C	Cryoablation	10mg/kg	10

E	Intrahepatic cholangiocarcinoma	RFA	10mg/kg	20
---	------------------------------------	-----	---------	----

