3.2 SCHEDULE

- Day 1: Tremelimumab IV every 4 weeks x 6 doses and then every 12 weeks for 2 years or until disease progression whichever comes first.
- Day 36 [+/- 96 hours]: RFA or TACE.
- Restaging CT /MRI scan every 8 weeks to evaluate TTP in target lesion. (Both standard RECIST and Immune-related Response Criteria [irRC] will be employed).
- Dose: (Cohort A only): Initially three to six patients will be treated at 3.5mg/kg (with subsequent dosing also at 3.5mg/kg) prior to enrolling to the 10mg/kg dose level. If a single patient experiences dose-limiting toxicity (DLT) related to the combination this cohort will be expanded to N=6 as per a standard 3+3 design. If 3.5mg/kg is established to be safe we will proceed to the 10mg/kg dose level. N=20 patients in cohort A will be treated at 10mg/kg.
- For Cohort A (BCLC Stage C patients): TACE or radiofrequency ablation (RFA) will be performed once only.
- For Cohort B (BCLC Stage B patients): TACE may be repeated (as per standard of care) on months 3, 7, and 13, and q6 months thereafter (if indicated).
- Cohort B will only be recruited following completion of the dose-escalation portion of Cohort A.

For Cohort E (BTC patients, status post prior chemotherapy with intrahepatic disease) RFA will be performed once only, also on Day 36 (+/- 96hrs).

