3.4.2 Treatment

The treatment schema for both cohorts is identical with the exception of the fact that in cohort B TACE may be repeated (as per standard of care) on months 3, 7, and 13, and q6 months thereafter (if indicated).

Patients in Cohort B will only be recruited following completion of the dose-escalation portion of Cohort A and will be treated at the dose level which has been determined to be safe in that cohort.

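### The re-induction rules give two different tremelimumab doses for a few Dose Level 1 patients, and two different answers on RFA for Cohort B

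*Combined protocol and SAP*

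**What the plan says.** **Dose.** Section 3.3.4 offers re-induction "using Tremelimumab at the assigned dose and schedule: i.e. 10mg/kg monthly for 6 months followed by maintenance 3-monthly Tremelimumab". Section 2.1.3.4 says "Patients will be treated at the same dose of Tremelimumab as they previously received" and then adds one exception: "For patients on Dose Level 1 who had already satisfied criteria for escalation to 10mg/kg they will be re-treated at 10mg/kg". Section 3.3.4 closes by requiring that the 2.1.3 criteria be met, so both statements apply to the same patient. The escalation criteria are in 3.3.2: at least 16 weeks of protocol therapy, criteria for continuing therapy met, and no toxicity above Grade 2 attributable to tremelimumab.

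**Procedure.** Section 3.3.4 calls for a repeat ablative procedure on Day 36 and says "This may be either an RFA or TACE depending on the opinion of the interventional radiologist". Section 2.1.3.6 likewise names TACE or RFA and sets no limit by cohort. For Cohort B, the précis and 3.1 say "They will not receive RFA". The closing paragraph of 2.1.3 says that re-induction follows the treatment criteria of the main study. Section 3.4.2 says "The treatment schema for both cohorts is identical with the exception of the fact that in cohort B TACE may be repeated".

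**The concern.** Two teams reading different sections could give the same re-inducted patient a different dose or, in Cohort B, a different procedure. This is first a question of what patients may receive.

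It also affects reporting. Section 8 does not mention re-induction. Section 8.3 tabulates toxicity by grade and foresees informal comparisons between procedures, and 8.1 evaluates Cohort A at 10 mg/kg as separate RFA and TACE groups of 10. Overall survival is a secondary endpoint (1.1.2), so follow-up runs past re-induction, and 2.1.3 sets no limit on the number of re-inductions. A patient who changes dose or procedure at re-induction would be reported with no rule for attributing what follows.

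**Working it through.** The plan gives no figure to reproduce here. The check is a comparison of passages with simple counting.

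**1. Who gets two different doses?**

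| Patient | By 2.1.3.4 | By 3.3.4 |
|---|---|---|
| Treated at 10 mg/kg from the start | 10 | 10 |
| Dose Level 1, escalation criteria met (escalated or not) | 10 | 10 |
| Dose Level 1, escalation criteria not met | 3.5 | 10 |

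Only the last row conflicts. The ratio is 10 / 3.5 = 2.86.

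**2. How many patients can be in that row?** Dose Level 1 has 3 to 6 patients. Under 3.3.2 it grows from 3 to 6 only after a DLT, and 2.1.3.2 bars from re-induction anyone with a related DLT. So the maximum is 3 without expansion, or 6 − 1 = 5 with it.

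**3. Can the row be reached?**

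- *By time.* Stable disease of at least 3 months (3 × 52/12 = 13 weeks) can qualify for re-induction, while escalation needs 16 weeks of therapy. The planned calendar nearly closes this gap. With scans every 8 weeks, disease control at week 8 puts first progression at week 8 + 8 = 16 or later. Confirmation under Appendix C comes at least 4 weeks after that, at week 20 or later. In the maintenance route, the sixth 4-weekly dose falls 5 × 4 = 20 weeks after the first. Progression before week 16 after 13 weeks of control would need an off-schedule scan.
- *By toxicity.* A Grade 3 endocrine event that is asymptomatic and controlled on hormone replacement may continue on drug (3.9.2). With hormone levels within normal limits it is not a DLT (3.7.2), so it does not by itself bar re-induction under 2.1.3.2. It is nevertheless above Grade 2, so while present it fails the escalation condition in 3.3.2. Full eligibility must be met again (2.1.3.5), including recovery of earlier toxicity to Grade 1 or baseline (2.1.1.9). The conflict therefore concerns a patient whose event blocked escalation and has since settled.
- *By continuance.* The plan does not say whether the continuance criteria count as met in a patient who is progressing.

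The row is small but not empty.

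**4. Cohort B.** There are two readings:

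- Re-induction is open to Cohort B. The 2.1.3 criteria name no cohort, and 3.4.2 makes the schema the same as Cohort A apart from repeat TACE. Section 3.3.4 then permits RFA, while 3.1, carried into re-induction by the closing paragraph of 2.1.3, forbids it.
- Re-induction is for Cohort A only, because 3.3.4 sits under the Cohort A heading. No sentence says so.

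Either way, wording has to be added or changed.

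**The case against.** The strongest reply is that 3.3.4 is shorthand. It speaks of the assigned dose, gives 10 mg/kg because nearly everyone is at that level, and defers to 2.1.3, where the specific rule is found. The patients in conflict are also very few. Drug-related events of Grade 3 or higher generally end treatment (3.9.2), and patients taken off for toxicity cannot be re-inducted. Both points have force and keep the dose conflict narrow. They do not remove it: 3.3.4 states a number, and the endocrine route passes through the plan's own exceptions.

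A second reply is that little in the analysis depends on this. Three-dose feasibility is already decided (8.1). DLTs are confined to the first 8 weeks. Six-month stable disease, response and progression-free survival are settled at or before the progression that triggers re-induction. This stands. It leaves overall survival and late toxicity, and no comparison of survival by dose is planned.

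A third reply is that 3.3.4 belongs to Cohort A and so does not touch Cohort B. That may be the intent, but the eligibility section is not limited in that way.

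**Conclusion.** The re-induction text needs reconciling on two points: dose for at most 5 Dose Level 1 patients (a 2.86-fold difference), and RFA for any re-inducted Cohort B patient. The documents do not give the number re-inducted. The figure of 5 assumes that expansion to 6 follows 3.3.2, that is, only after a DLT. The Cohort B conflict assumes that re-induction is open to that cohort. The matter bears on safety and on the attribution of late events, not on sample size, power or any decision rule.

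A reader might infer more than the documents support:

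- *That Cohort A cannot have a second procedure.* Section 3.2 says "TACE or radiofrequency ablation (RFA) will be performed once only", but 1.2.6 expressly plans for one patient to have both TACE and RFA, and 3.3.4 calls the procedure a repeat. The natural reading is once per treatment course, so this is a wording point.
- *That Cohort E has no suitable re-induction procedure.* Its procedure is RFA, which is on the list.
- *That Cohort D is contradicted.* Cryoablation is not listed for re-induction, but 3.6 does not mention re-induction at all. This is silence, not two competing rules.
- *That all enrolled patients are exposed to the conflict.* Re-induction requires earlier disease control or entry to maintenance, confirmed progression, no related DLT and renewed full eligibility.
- *That survival should be censored at the start of re-induction.* Re-induction follows progression in patients selected for earlier disease control, so such censoring would be informative and is not advised.

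**What to change.** Reconcile 3.3.4 with 2.1.3.4, 2.1.3.6, 3.1 and 3.4.2 so that there is one re-induction dose rule and one procedure rule, and state which cohorts may be re-inducted. Which dose and which procedure apply is for the sponsor to decide. While editing, make clear in the précis and 3.2 whether the limit of one procedure in Cohort A applies per treatment course.

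In 8.3, add that adverse events from the start of re-induction are tabulated separately, by the dose and procedure actually given.

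The cost is wording in a handful of sections and one extra safety table. It needs no new data and no change to sample size.

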3.3.4.1 Tumor Biopsies

If a patient opts to undergo re-induction therapy we would like to perform pre- and post-re-induction tumor biopsies to better understand the role of emerging resistance to anti-CTLA4 therapy. These would occur prior to re-induction (≤ 2 weeks prior to starting) and then during the interventional radiologic procedure.

3.4 COHORT B

3.4.1 Definition

The definition of Cohort B is as follows:

Cohort B (N=20):

- HCC, Barcelona Clinic Liver Cancer (BCLC) Stage B;
- Child Pugh A/B7;
- No available surgical (i.e. transplantation or hepatic resection) or curative ablative option.
- Disease amenable to TACE

3.4.2 Treatment

The treatment schema for both cohorts is identical with the exception of the fact that in cohort B TACE may be repeated (as per standard of care) on months 3, 7, and 13, and q6 months thereafter (if indicated).

Patients in Cohort B will only be recruited following completion of the dose-escalation portion of Cohort A and will be treated at the dose level which has been determined to be safe in that cohort.

3.5 COHORT C

This cohort, designed to evaluate tremelimumab in combination with external beam radiation was removed with amendment I.

3.6 COHORTS D-E

Once safety is established for the initial concept of combining anti-CTLA4 with ablative procedures (RFA and TACE), we will similarly explore feasibility of tremelimumab at the same dose and schedule in 2 additional cohorts (denoted D-E) evaluating tremelimumab in

combination with cryoablation in HCC (cohort D) and with RFA in a cohort of patients with biliary tract carcinoma (cohort E).

- For these additional cohorts, the dose (10mg/kg) and schedule of tremelimumab will be as per cohorts A and B. The timing of the interventional procedure will also be identical.
- Cohort Definition: Cohort D will have the same definition as Cohort A above:
Advanced stage HCC, BCLC group C
Patients must have progressed on, been intolerant of prior sorafenib therapy.
Child Pugh A/B7
No available surgical option (i.e. transplantation or hepatic resection) or curative ablative option.
Disease amenable to cryoablation
- Cohort E will contain BTC patients as specified in the eligibility criteria.
- For cohorts D-E no dose escalation will occur. All patients will receive tremelimumab at 10mg/kg at the same schedule established as safe and feasible in Cohort A of the study. However, protocol stopping rules will apply as outlined in Section 3.3.

3.7 DOSE LIMITING TOXICITIES

3.7.1 Definition of Dose-limiting Toxicities (DLTs):

A DLT is defined as a \geq Grade 3 adverse drug reaction (ADR) according to the NCI-CTCAE v4.0, that is possibly, probably, or definitely related to the combination of Tremelimumab with either TACE or RFA, occurring during the DLT evaluation period except for any of the following outlined in section 3.6.2. ADRs are defined in this trial as any AEs suspected to be related to Tremelimumab by the investigator. Evaluation period for Dose-limiting Toxicities (DLT) will extend for the first 8 weeks of the study.

Treatment-related SAE will be ascribed as related to drug except where a clear relationship to the underlying disease or recognized co-morbidities is evident. For this trial, the MTD is defined as the highest dose where < 2 of 6 subjects experience a DLT.

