3.3.2 Treatment

Three patients will be treated at 3.5mg/kg (with subsequent dosing also at 3.5mg/kg i.e. no inpatient dose escalation) prior to enrolling to the 10 mg/kg dose level. If a single patient experiences dose-limiting toxicity (DLT) related to the combination of TACE/RFA and

Tremelimumab this cohort will be expanded to N=6 as per a standard 3+3 design. If 3.5mg/kg is established to be safe we will proceed to the 10 mg/kg dose level. N=20 patients will be treated at 10 mg/kg to evaluate the feasibility endpoint, provided no more than 2 of 3-6 patients have a DLT at this level.

Dose level	Tremelimumab dose (mg/kg)	N
1	3.5	3-6
2	10	20

- The 3.5 mg/kg cohort will have at least 3 patients to evaluate for toxicity to establish MTD for the combination of Tremelimumab with either TACE or RFA. Three patients will be treated at this dose level. The descriptions and grading scales found in the revised NCI Common Terminology Criteria for Adverse Events (CTCAE) version 4.0 will be utilized for AE reporting. If none of the three patients at the 3.5 mg/kg dose level experiences dose-limiting toxicity (DLT), accrual to DL2 will proceed to the 10mg/kg cohort. If one of three patients treated at a dose level experiences DLT that is considered to be at least possibly related to the combination of Tremelimumab with either TACE or RFA, then three more patients will be enrolled at that same level. If the incidence of DLT among those six patients is one in six, then we will proceed to 10 mg/kg. If two or more of the six patients experience DLT, then the MTD is considered to have been exceeded.
- Evaluation period for Dose-limiting Toxicities (DLT) will extend for the first 8 weeks of the study.
- Following completion of the dose escalation portion of the study Tremelimumab will be administered at the MTD at the same schedule. A total of 20 patients will be treated in cohort A at the MTD, not including those patients treated at the lower doses.
- For patients on Dose Level 1 who have completed at least 16 weeks of protocol therapy, we will consider dose escalation to 10mg/kg if criteria for continuance of therapy are met and the patient does not have >Grade 2 toxicity attributable to tremelimumab.

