3.7.2 Exclusions to Dose Limiting Toxicities

- Grade 3 infusion-related reaction resolving within 6 hours and controlled with medical management.
- Any Grade 3/4 non-hem toxicity that occurs in the first 10 days after RFA or TACE and which is an expected toxicity of the procedure in the opinion of the PI. These symptoms include, but are not limited to, fevers/rigors, pain, fatigue and nausea.
- Any grade 3 immune-mediated adverse event (including but not limited to Grade 3 diarrhea, Grade 3 skin toxicity, or Grade 3 liver enzyme elevation) that improves to \leq Grade 2 within 1 week of onset with supportive care (which may include systemic corticosteroids).
- Nausea and vomiting Grade 3 will only be considered dose-limiting if it is refractory to anti-emetic therapy and unable to be corrected to Grade 1 or less within 48 hours.

- Grade 3 rise in creatinine, not corrected to Grade 1 or less after 2 liters of intravenous fluids within 24 hours, will be considered dose limiting.
- Single laboratory values out of normal range that are unlikely related to trial treatment according to the investigator, do not have any clinical correlate, and resolve within 7 days with adequate medical management.
- Transient (≤ 24 hours) Grade 3 fatigue, local reactions, headache, nausea, emesis that resolves to \leq Grade 1.
- Grade 4 elevation in transaminase elevation that improves to \leq Grade 2 within 10 days of onset with supportive care.
- Grade 3 endocrinopathy that is managed with or without systemic corticosteroid therapy and/or hormone replacement therapy and the following criteria are met:
 - The subject's hormone levels are within normal limits
 - The subject is asymptomatic
- Grade 3 inflammatory reaction attributed to a local antitumor response (eg, inflammatory reaction at sites of metastatic disease, lymph nodes, etc.)

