8.1 COHORTS A AND B

Relative to the feasibility endpoint, this will be decided in Cohorts A and B; all patients enrolled into Cohorts A and B at the 10 mg/kg dose level will be considered as one group for feasibility evaluation. Feasibility will be evaluated in the first 20 evaluable patients enrolled in in these two cohorts on this trial at the 10mg/kg dose level following a dose-escalation phase of 3-6 patients treated at 3.5mg/kg dose level. The safety of the 10 mg/kg dose level will be evaluated in the first 3-6 patients treated at that dose. If there are 2 or more DLTs among the first 3-6 patients treated at this level, then accrual would stop. Regarding feasibility, it would be desirable if the fraction of patients who could receive three doses of the monoclonal antibody were consistent with 80% or higher and greater than 50%. With 20 evaluable patients, if there are 14 or more patients who are able to receive three doses of the monoclonal antibody, then there is a 5.8% probability of this being true if the true probability of an individual patient being able to receive this much antibody were 50% and there is a 91.3% probability of this being true if the true probability for an individual were 80%. Thus, 14 or more out of 20 patients receiving three doses of antibody would provide strong evidence that it is feasible to administer this antibody in a substantial fraction of patients, consistent with 80% or more and this would be considered a successful outcome for the trial.

Prior to amendment G, administration of three doses has been determined to be feasible based on the first 20 total patients enrolled and the feasibility evaluation was considered to have ended at that point. Evaluations for clinical efficacy will be the primary objective from this point forward.

With amendment G, there will be 20 patients enrolled in cohort A at 10mg/kg (10 receiving RFA and 10 receiving TACE).

Each of these sub-cohorts will be evaluated for efficacy as follows. In each sub-cohort of 10 patients the trial will have 82% power to rule out 15% 6 month as the proportion stable at 6

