8.2 COHORTS D- E

With amendment F, one additional cohort of N=10 patients will be added to explore the immune effects of combining tremelimumab with cryoablation (Cohorts D) and one cohort with RFA in a BTC population. Thus, there will be 2 new cohorts added at this time for a total of 20 additional patients. Results to date from cohorts A and B suggest that the overall procedure is very likely to meet its feasibility goal since 9/10 patients have done so as of the date this amendment was constructed. As a result, the goal of the two new cohorts is to determine in a preliminary fashion if the treatment proposed in each cohort is able to offer clinical benefit to patients. Data on similar patients suggests a median time to progression of approximately 2 months, and approximately 10-15% would have stable disease at 6 months. It would be a very meaningful improvement if the treatment proposed could be associated with results which were consistent with 50% of patients having stable disease at 6 months. With the goal of keeping the trial small, in each cohort of 10 patients the trial will have 82% power to rule out 15% as the proportion stable at 6 months in favor of 50% being stable at 6 months, with each evaluation assuming that a one-sided 0.10 significance level exact binomial test would be performed. As a practical matter, 10 patients will be enrolled in each of the two cohorts and if there are 3 patients in 10 who are able to have stable disease at a 6 month evaluation, then the lower one-sided 90% confidence bound for 3/10 is 11.6% (the two sided 80% confidence interval extends from 11.6% to 55.2%). Similarly, with 4 in 10 with stable disease at 6 months, the lower one-sided 90% confidence bound for 4/10 is 18.8% (the two sided 80% confidence interval extends from 18.8% to 64.6%). Thus, in any given cohort, 3 or 4 patients attaining stable disease at 6 months would rule out 10-15% as the fraction who would do so, with 90% one sided confidence.

With amendment G, cohort E (cholangiocarcinoma patients) will be expanded to a total of 20 patients. This cohort will have 97% power to rule out 15% as the proportion stable at 6 months in favor of 50% being stable at 6 months, with the evaluation assuming that a one-sided 0.10 significance level exact binomial test would be performed. If there are 6 patients in 20 who are

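### Cohort D (tremelimumab 10 mg/kg plus cryoablation, N=10) has no prespecified cohort-level threshold that acts on Grade 3 dose-limiting toxicities

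*Combined protocol and SAP*

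**What the plan says.** **Objective.** The précis puts cryoablation in the trial's main safety and feasibility objective. Section 1.1.3.2 lists safety and feasibility with cryoablation as an exploratory objective.

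**DLT definition.** Under 3.7.1 a DLT is a Grade 3 or higher drug reaction "that is possibly, probably, or definitely related to the combination of Tremelimumab with either TACE or RFA, occurring during the DLT evaluation period", within the first 8 weeks. Section 3.7.2 excludes expected toxicity of the procedure: "Any Grade 3/4 non-hem toxicity that occurs in the first 10 days after RFA or TACE". Neither section names cryoablation.

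**DLT counts.** Section 8.1, headed Cohorts A and B, says of the 10 mg/kg level: "If there are 2 or more DLTs among the first 3-6 patients treated at this level, then accrual would stop". Section 3.3.2, for Cohort A, lets treatment at 10 mg/kg proceed "provided no more than 2 of 3-6 patients have a DLT at this level".

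**Cohorts D and E.** Section 3.6 opens them at 10 mg/kg without escalation, once safety is established for RFA and TACE, and adds: "However, protocol stopping rules will apply as outlined in Section 3.3". The part of 3.3 with that title is 3.3.3. It halts the protocol temporarily for one attributable Grade 5 event or for "Two occurrences of grade 4 toxicity by the NCI-CTCAE version 4.0 attributable to the treatment regimen". Section 8.2 states that "the goal of the two new cohorts is to determine in a preliminary fashion if the treatment proposed in each cohort" offers clinical benefit, and it sets only stable-disease criteria.

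**The concern.** Cohort D is this trial's first use of tremelimumab with cryoablation, and it starts at the full dose. For the first patients given 10 mg/kg with RFA or TACE, the plan did not rely on clinical judgment and the Grade 4/5 halts alone. It added an early DLT count. That count does not reach Cohort D, for two separate reasons: the rule is written for other cohorts, and a cryoablation-related event is not a DLT as defined.

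If several Cohort D patients had Grade 3 toxicity related to the combination, the protocol would not say whether accrual should pause. The decision would be made case by case, after the events were known, in a cohort of ten.

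**Working it through.** **1. Which rules reach Cohort D**

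| Rule | Written for | Acts on Grade 3? | Reaches Cohort D? |
|---|---|---|---|
| DLT definition, 3.7.1 | TACE or RFA | Yes | No, cryoablation not named |
| DLT count, 3.3.2 | Cohort A | Yes | No |
| DLT count, 8.1 | Cohorts A and B at 10 mg/kg | Yes | No |
| Protocol halts, 3.3.3 | Whole protocol | No | Yes |
| Hold or discontinue, 3.9 | Individual patient | Yes | Yes, but no cohort threshold |
| Team review, 7.5.1; IRB table, 7.2.2; tabulation, 8.3 | All patients | Yes | Yes, but no threshold |

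**2. The plan's own figure.** The only design calculation that covers Cohort D is 82% power in 8.2 (15% against 50% stable at 6 months, N=10, one-sided 0.10 exact test). Requiring 4 or more of 10 gives P(X≥4) = 0.050 at 15% and 0.828 at 50%, so the figure reproduces. The documents give no operating characteristics for any DLT or stopping rule, and no DLT rate for this combination. Every toxicity rate below is therefore an assumption.

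**3. The 8.1 count run as a 3+3.** With DLT rate p:

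P(stop) = P(X≥2 of 3) + P(X=1 of 3) × [1 − (1−p)³]

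| p | First term | Second term | P(stop) |
|---|---|---|---|
| 10% | 0.028 | 0.066 | 0.094 |
| 20% | 0.104 | 0.187 | 0.291 |
| 30% | 0.216 | 0.290 | 0.506 |
| 40% | 0.352 | 0.339 | 0.691 |

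**4. The existing Grade 4 halt.** Let q be the chance that a patient has an attributable Grade 4 event. From Cohort D alone (n=10), P(X≥2) = 0.086 at q=5% and 0.264 at q=10%. The halt is protocol-wide. If one Grade 4 event had already been counted in another cohort, a single one in Cohort D would trigger it: 1 − 0.95¹⁰ = 0.401 at q=5%. It also has no 8-week limit, so later events count too.

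**5. Both rules together in Cohort D (N=10).** Exact enumeration: each patient has no DLT, a Grade 3 DLT with probability p−q, or a Grade 4 DLT with probability q. Grade 5 and other cohorts are ignored.

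| q | Grade 4 halt alone | With 3+3: p=10% | 20% | 30% | 40% |
|---|---|---|---|---|---|
| 5% | 8.6% | 14.4% | 32.5% | 52.7% | 70.4% |
| 10% | 26.4% | 26.4% | 40.7% | 58.0% | 73.5% |

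The table simplifies in two ways. It uses one q for the 8-week window and for the whole of treatment, and it counts every Grade 4 event as a DLT, although 3.7.2 exempts some.

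**6. What the window covers.** Section 3.2 schedules "Day 36 [+/- 96 hours]: RFA or TACE", and 3.6 makes the timing identical for Cohort D. The procedure therefore falls on Days 32 to 40. With the window ending on Day 56, 56 − 40 = 16 to 56 − 32 = 24 days follow it.

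**7. Length of a pause.** 8 weeks is 56/30.4 ≈ 1.84 months. At up to 2 patients a month across the trial (8.4), that is 1.84 × 2 ≈ 3.7 enrolment slots.

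**The case against.** **This is a reasoned design choice.** The DLT counts are dose-finding gates. Section 3.6 explains that D and E open only after safety is established, at a dose already found safe, with the protocol halts in force. Cohort A and B patients enrolled after the first 3–6 at 10 mg/kg also rely on those halts. This parity is real, and it answers the point for Cohort E. It does not answer it for Cohort D, because safety was established with RFA and TACE, not cryoablation.

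**Cryoablation has its own safety data.** Section 1.2.8 cites a randomized trial of 360 patients with major complications in 3.9% after cryoablation and 3.3% after RFA. That supports substituting the procedure, but the comparison concerned the procedures and does not test the combination with tremelimumab.

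**The cross-reference to Section 3.3 might include the count in 3.3.2.** The phrase used is the title of 3.3.3, and 3.3.2 is written for Cohort A. Even on the broad reading, a cryoablation event would still fall outside the DLT definition.

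**The gain is smaller than a simple comparison suggests.** This stands in part. The 8.6% and 26.4% are lower bounds. The largest gains need DLT rates of 30–40%. The only figure for this dosing regimen in the documents is 27% Grade 3–4 events in melanoma without ablation (1.2.5), before the 3.7.2 exclusions.

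**The rule barely tests the procedure.** Also partly right: only 16–24 days follow it, and expected procedural toxicity in the first 10 days is excluded. The rule for Cohorts A and B has the same limit.

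**Stronger readings to avoid.** A reader might infer that Cohort D has no safety rule, or no chance of being halted. Neither holds, because the Grade 4/5 halts and the patient-level actions in 3.9 apply. A reader might also infer that Cohort E needs the same gate. It repeats Cohort A's drug, dose, timing and RFA procedure, and its events already fit the DLT definition. A second gate there is a trade-off, not a gap to close. Nothing in the documents shows that toxicity in Cohort D is expected to be excessive.

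**Conclusion.** The point holds for Cohort D only. The text leaves a combination whose safety is a stated objective without a matching DLT definition and without any cohort-level threshold for Grade 3 DLTs.

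The size depends on assumed rates. Where toxicity is mainly Grade 3, the gain is large: at a 30% DLT rate with Grade 4 at 5 points, the chance of stopping rises from 8.6% to 52.7%, counting Cohort D alone. Where Grade 4 makes up most of the toxicity, the gain is small or nil: at a 10% DLT rate that is all Grade 4, it stays at 26.4%. Grade 4 events in other cohorts, late events or a Grade 5 event would raise the current figures and narrow the difference. This is a cheap safety improvement. It does not mean that patients are unprotected.

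**What to change.** Four edits, all limited to Cohort D:

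- **3.7.1:** list the procedures as *TACE, RFA or cryoablation*.
- **3.7.2:** list them as *RFA, TACE or cryoablation*.
- **8.2:** add *In Cohort D, if 2 or more DLTs occur among the first 3–6 patients, accrual to Cohort D stops*, and say that it runs as a 3+3 with 8 weeks of observation. Use the 8.1 threshold, which agrees with the MTD definition in 3.7.1 (fewer than 2 of 6). Do not borrow the 3.3.2 wording, which lets exactly 2 DLTs pass.
- **3.6:** replace the reference to Section 3.3 with *Section 3.3.3 and, for Cohort D, the DLT rule in 8.2*.

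The Grade 4/5 halts stay as they are.

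**Cost.** No extra patients or visits. Accrual to Cohort D may pause for up to 8 weeks after the third patient, and again after the sixth if the first three include exactly one DLT. Each pause affects at most about 4 slots trial-wide, which other open cohorts can use. There is a 9% chance of stopping when the true DLT rate is only 10%. With 16–24 days of observation after the procedure, the rule remains a limited check on cryoablation itself.
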